9.4.4 Sensitivity Analyses

If the assumption of similarity between the placebo cohorts is supported and placebo cohorts can be pooled, a sensitivity analysis will be performed on the percent change from baseline to Week 16 in PASI score using a Bayesian Emax dose response model on the pooled cohorts in the following form:

$$\text{Response} = E0 + Emax \cdot f(\text{dose})$$

Three possible models will be considered for the $f(\text{dose})$:

- Log-linear: $f(\text{dose}) = \log(\text{dose}+0.01)$, where 0.01 is an offset to allow the model to fit for zero dose (placebo)
- 3-parameter model: $f(\text{dose}) = \text{dose}/(\text{dose}+\text{ED50})$
- 4-parameter model: $f(\text{dose}) = \text{dose}^{\text{slope}}/(\text{dose}^{\text{slope}} + \text{ED50}^{\text{slope}})$

Where:

- Response = Percentage change from baseline in PASI at Week 16
- E0 = the response at dose = 0 (placebo)
- Emax = the maximal response over placebo
- ED50 = the dose that yields 50% of the maximal response
- slope = the dose-response slope parameter

Dose will be fitted as a continuous variable with values of 0, 1, 4 and 10 used to denote the number of active capsules taken by each of the treatment groups.

An inverse gamma prior with shape of 0.001 and scale of 0.001 will be used for the residual variance. Normal, non-informative priors will be used for the E0 and Emax parameters with mean 0 and SD 1000. A functional uniform prior (FUP) will be used, when required, for the ED50 and slope parameters where the prior density of the FUP is based on all the parameters in the model. For the FUP, the density will be calculated for values of dose from 0.01 to 10.01 in steps of 1. The use of a FUP shrinks the dose response towards a flat line throughout the dose range, therefore providing more conservative estimates of the dose-response relationship compared to maximum likelihood ([Bornkamp 2014](#)).

Parameters will be blocked so that the MCMC procedure samples from E0 and Emax first, then the ED50 and slope parameters and finally the residual variance parameter.

100,000 MCMC samples will be generated with a thin of 20 to leave 5000 retained samples after a burn-in of 10,000 samples. The number of samples or thin may be increased to reduce the ratio of the MCSE to the posterior SD, as deemed necessary.

The best-fitting (lowest DIC) of the three models will be selected and based on the selected model, the posterior mean with associated 95% HPD CrI will be displayed for the percentage change from baseline in PASI score at Week 16 and the pairwise treatment differences between each active dose and the pooled placebo group. Posterior probabilities will also be presented for the pairwise treatment differences between each active dose and placebo being less than 0%, -20%, -30% and -50%.

A figure will be presented of the fitted mean dose response model with the 95% HPD CrI for all possible doses (0 to 10 in steps of 0.5) in the dose range, overlaid with the Week 16 posterior means and 95% HPD CrI for the MMRM model specified in [Section 9.4.3](#).

If any of the results of the analyses using the supportive estimands are found to differ substantially from the primary estimand for the main analytical approach using the MMRM, this sensitivity analysis will be repeated using the supportive estimands.

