6.4.3.4 Analysis of Fecal Microbiome

The microbiome composition of stool samples will be assessed by 16S ribosomal RNA sequencing, which looks at the diversity and abundance of microbes in the colonic microbiome (Human Microbiome Project Consortium 2012). EDP1815 is not expected to alter the composition of the microbiome, but it is being evaluated as a safety biomarker.

7 Statistical Considerations

Analysis methods for key endpoints are described below. Further details on all analyses will be described in the SAP.

No formal hypothesis will be tested. A model-based probability inference approach in a Bayesian framework will be used to guide decision-making around dose selection. Posterior estimates and 95% CrI for the difference between each active dose and placebo will be produced for relevant primary and secondary endpoints.

Unless otherwise specified, missing data will be considered as missing at random and will be accounted for using mixed models for repeated measures, with all time points collected for the relevant endpoint included in the model. This includes data which is excluded due to collection after treatment discontinuation or after a protocol deviation as applicable to the definition of the estimands used in the analysis.

The primary analysis for the study will occur after all participants have completed 4 weeks of follow-up after their last dose of study medication (end of Part A). The final analysis for the study will occur when all participants have completed the required relapse and rebound follow-up period of up to 24 weeks post-treatment (end of Part B).

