The dose-response model will be fitted to the data using Bayesian techniques with noninformative priors for E_0 and E_{max} and an FUP for ED50 (3- and 4-parameter models only) and the slope parameter m (4-parameter model only). The rationale for this choice of inference is that the FUP shrinks the dose response towards a flat line throughout the dose range, therefore providing more conservative estimates of the dose-response relationship compared to maximum likelihood (Bornkamp 2014). The models will be fully described in the SAP.

Based on the selected model, the posterior mean with associated 95% HDP CrI, for the difference from placebo for each active dose will be produced for the pairwise differences between each active dose and placebo, together with the posterior mean and 95% HDP CrI of the treatment difference from placebo for each active dose and posterior probabilities that difference from placebo is less than 0, -20%, -30%, and -50%. A further sensitivity analysis will be performed on the dose response model, in which participants who withdrew from study drug due to treatment will have their Week 16 percentage change from PASI imputed as 100% after study drug was discontinued.

Percent change from baseline in PASI score will be summarized by visit.

All summaries and analyses defined above for the primary estimand will be repeated using the subgroups defined in Section 7.5.

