7.6.2 Analysis of Secondary Efficacy Endpoints

All secondary analyses will be performed either using the pooled placebo group if the assumption of similarity for the placebo cohorts is considered appropriate or using the 3 cohort-level placebo groups if it is not considered appropriate.

Unless otherwise specified, all secondary analyses will be performed on the mITT set, excluding data collected after treatment discontinuation, without consideration of any protocol deviations. Dose will be treated as a categorical variable and no dose response modelling will be done. Comparisons of interest will be between individual EDP1815 doses and placebo. All p-values, posterior probabilities, CI, and CrI calculated will be considered as descriptive with no further adjustments for multiplicity performed.

Data will be analyzed as collected and no imputation of missing data will be performed.

The covariates selected for the Bayesian MMRM analysis for the primary estimand will also be used in all other analytical models including covariates.

Mean percentage change from baseline in PASI score at Weeks 4, 8, and 12 will be analyzed as part of the MMRM for the primary estimand. The same statistics produced for the Week 16 time point will also be produced at Weeks 4, 8, and 12.

The following secondary endpoints will be analyzed in the same manner as described for the primary analysis:

- Mean absolute change from baseline in PASI score at Weeks 4, 8, 12, and 16
- Mean percentage change from baseline in LSS at Weeks 4, 8, 12, and 16
- Mean absolute change from baseline in LSS at Weeks 4, 8, 12, and 16
- Mean percentage change from baseline in PGA×BSA at Weeks 4, 8, 12, and 16
- Mean absolute change from baseline in PGA×BSA at Weeks 4, 8, 12, and 16

- Mean percentage change from baseline in DLQI score at Weeks 4, 8, 12, and 16
- Mean absolute change from baseline in DLQI score at Weeks 4, 8, 12, and 16
- Mean percentage change from baseline in mNAPSI total score at Weeks 4, 8, 12, and 16
- Mean absolute change from baseline in mNAPSI total score at Weeks 4, 8, 12, and 16

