7.3 Missing Data

Missing efficacy data such as individual item scores will be dealt with as detailed in [Section 5.3.3](#). Otherwise, no imputation of missing efficacy data will be performed, and the use of mixed models will account for missing data.

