9.4.3 Main Analytical Approach

Percentage change from baseline in PASI score at each visit will be summarised. Mean (+/- SD) percentage change from Baseline over time will be plotted in a figure. Also, waterfall plots will be created to show the ranked individual percentage change from Baseline at Week 16.

The primary analysis will be performed using a Bayesian mixed model for repeated measures (MMRM). The model will include parameters for treatment*visit and baseline PASI score*visit interactions and will not include an intercept.

Treatment will consist of 4 levels (all placebo, EDP1815 1 capsule, EDP1815 4 capsules and EDP1815 10 capsules) if the placebo pooling strategy is considered appropriate or 6 levels (Placebo 1 capsule, Placebo 4 capsules, Placebo 10 capsules, EDP1815 1 capsule, EDP1815 4 capsules, and EDP1815 10

capsules) if the placebo pooling strategy is not considered appropriate. Visit will consist of 7 levels (Weeks 1, 2, 4, 8, 12,16 and 20).

As described in [Section 9.2](#) additional covariates for baseline factors will be assessed using this model for inclusion in all efficacy models.

The priors for all parameters in the model will be non-informative and follow a normal distribution with mean 0 and SD 1000. The prior for the variance-covariance matrix will follow an inverted Wishart distribution with degrees of freedom equal to the number of visits and an identity scale matrix. The choice of Wishart distribution is based on it being the conjugate prior of the inverse-covariance matrix of a multivariate-normal random vector.

The model will be blocked so that the MCMC procedure samples from the treatment*visit parameters first, then the baseline*visit parameters, then any additional fitted covariates and finally the variance-covariance matrix.

100,000 MCMC samples will be generated with a thin of 20 to leave 5000 retained samples after a burn-in of 10,000 samples. The number of samples or thin may be increased to reduce the ratio of the Monte Carlo standard error (MCSE) to the posterior SD, as deemed necessary.

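### The SAP's only dose-response model uses observed Week 16 scores alone, so its missing-data rule does not cover it and it needs a stronger missingness assumption than the primary MMRM

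*SAP*

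**What the plan says.** SAP 9.4.4 plans the dose-response model only where placebo pooling is accepted: "a sensitivity analysis will be performed on the percent change from baseline to Week 16 in PASI score using a Bayesian Emax dose response model". The outcome is "Response = Percentage change from baseline in PASI at Week 16" and the mean is E0 + Emax·f(dose), with three candidate forms of f. The sampler "samples from E0 and Emax first, then the ED50 and slope parameters and finally the residual variance parameter", so there is one residual variance and no within-participant covariance matrix. No visit, baseline PASI or other covariate term is listed.

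The primary MMRM in SAP 9.4.3 is different: "The model will include parameters for treatment*visit and baseline PASI score*visit interactions and will not include an intercept". It uses every scheduled PASI visit from Week 1 to Week 20, and treats dose as a set of treatment levels.

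On missing data, SAP 7.3 says that, apart from item-level rules, "no imputation of missing efficacy data will be performed, and the use of mixed models will account for missing data". Protocol 7 (Statistical Considerations) opens its rule with "Unless otherwise specified, missing data will be considered as missing at random and will be" and goes on to name mixed models for repeated measures as the method. SAP 9.4.1 sets PASI scores taken more than 4 days after treatment discontinuation to missing.

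Protocol 7.6.1 planned one dropout check on the dose-response model, in which certain withdrawn participants "will have their Week 16 percentage change from PASI imputed as 100% after study drug was discontinued". SAP 9.4.4 does not contain that check, and Table 8 (changes from the protocol) does not mention its removal.

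**The concern.** Dose response at Week 16 is a secondary objective in both documents. No other analysis models it: the MMRM is categorical in dose, and Protocol 7.6.2 rules out dose-response modelling for secondary endpoints, where "Comparisons of interest will be between individual EDP1815 doses and placebo".

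A repeated-measures likelihood lets a participant who stops at Week 12 still inform the Week 16 mean through earlier scores, and is valid if missingness depends only on what was observed. A single-visit fit gives that participant no weight. Without baseline or earlier visits, it is valid only if, within each dose group, being observed at Week 16 is unrelated to the Week 16 outcome. The SAP does not state this stronger condition, and the general sentence in SAP 7.3 suggests the matter is already covered.

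A link between dropout and outcome is plausible from the documents. Under Protocol 4.2, treatment failure leads to discontinuation or withdrawal, and the 4-day rule then removes later scores. Loss could also differ by dose, since the cohorts take 1, 4 or 10 capsules and Protocol 5.9 anticipates tolerability problems from capsule load. At stake are the height and, to a lesser extent, the shape of the curve meant to inform dose selection.

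**Working it through.** **Inputs from the documents** (Protocol 7.3, SAP 6): difference 20 points, SD 25, 50 randomized per active dose and 75 to pooled placebo, at most 15% discontinuing, 42 active and 21 placebo evaluable per cohort, 5% level (taken as two-sided).

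**The plan's own figures reproduce.**
- Evaluable: 50 × 0.85 = 42.5 (42) and 25 × 0.85 = 21.25 (21).
- Pooled: SE = 25 × √(1/42 + 1/63) = 4.98; 20/4.98 − 1.96 = 2.06; power 98.0%, against the stated more than 95%.
- Within cohort: SE = 25 × √(1/42 + 1/21) = 6.68; 20/6.68 − 1.96 = 1.03; power 84.9%, against the stated more than 80%.

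**Who enters the curve.** 3 × 42 + 63 = 189 of 225 at the planned ceiling. The other 36 contribute nothing to it, whereas those with any earlier on-treatment score do contribute to the MMRM.

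**Size of possible bias.** The documents give no dropout pattern, so this rests on assumptions: 200,000 simulated participants per arm; SD 25 at each visit; correlation per 4 weeks of 0.6, 0.8 or 0.9; true Week 16 differences from placebo of −8, −14 and −20 for 1, 4 and 10 capsules; dropout after Week 8 or Week 12 depending on the last score, with an odds ratio per SD of 1, 2 or 4. Bias is in points on the active-minus-placebo difference using observed Week 16 scores only; a positive value means the effect is understated.

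| Dropout scenario | Any dose | 10 capsules |
|---|---|---|
| Unrelated to PASI, including unequal rates of 25/15/10/5% | about 0 | about 0 |
| One outcome-dependent mechanism in all arms, about 15% overall | +0.1 to +1.7 | +0.4 to +1.7 |
| Outcome-dependent; 25% placebo, 15/10/5% active | +0.9 to +4.7 | +1.7 to +4.7 |
| Outcome-dependent; 10% placebo, 10/15/25% active | +0.1 to −3.5 | −1.2 to −3.5 |
| Outcome-dependent, no true effect in any arm | about 0 | about 0 |

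An estimator using the earlier visits stayed within 0.1 point throughout. Against the 20-point target, 1.7 is 8.5% and 4.7 is 23.5%. Against the pooled SE of 4.98, they are 0.34 and 0.94 of a standard error.

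**Effect on the fitted curve.** A 3-parameter Emax curve was fitted at correlation 0.8 and odds ratio 4:
- Placebo losing most: fitted effects −5.2/−11.7/−15.5, against −7.0/−14.9/−19.3 with complete data. The 4-to-10-capsule ratio is 11.69/15.50 = 0.75, against 14.91/19.30 = 0.77, so mainly the height changes.
- High dose losing most: −6.5/−15.8/−22.0, against −7.0/−14.9/−19.2. The ratio is 15.76/21.98 = 0.72, against 14.89/19.17 = 0.78, so the curve steepens at the top.

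**Would the planned checks show it?** SAP 9.4.4 repeats the dose-response model under the supportive estimands only if a supportive MMRM differs substantially (undefined) from the primary MMRM. That compares one MMRM with another, never the Week-16-only fit with the MMRM. At the interim the trigger cannot fire, because the supportive MMRM tables are not flagged for it while the dose-response table is.

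**The case against.** The strongest reply is that this is a sensitivity analysis (supplementary in the protocol), run only if placebo is pooled, and that the primary MMRM already estimates every dose using all visits and baseline PASI. The SAP overlays the fitted curve on the MMRM Week 16 means, and Figure 14.2.1.5 plots completers against discontinuers. Protocol 7 also qualifies its missing-data rule with an exception for anything otherwise specified.

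Much of this stands, and it limits the importance of the point. The overlay would reveal a large gap, although a reader could not tell curve misfit from missing data. The protocol's exception does not help, because SAP 9.4.4 specifies no alternative handling.

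Three stronger readings are tempting and are not supported:

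- **That the curve is biased by dropout.** The documents give a 15% ceiling and no split by arm. Bias is about 0 if dropout is unrelated to PASI. In a separate run with true effects of −8/−18/−20 and no arm above 15%, the 10-capsule effect of −20 appeared as −19.2 (odds ratio 2) or −18.2 (odds ratio 4).
- **That every dose effect shrinks.** The sign reverses when the higher doses lose more participants, which capsule load makes conceivable.
- **That dose-against-dose intervals come out 29% too wide because only placebo-referenced intervals are reported.** Combining two such intervals as if independent gives a half-width of 1.96 × √2 × 4.98 = 13.8, against 1.96 × 25 × √(2/42) = 10.7 for the direct contrast. But SAP 9.4.3 also reports each group's Week 16 mean with its interval. Each half-width is 1.96 × 25/√42 = 7.56, and √2 × 7.56 = 10.7, so nothing is lost.

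Nor does omitting baseline PASI from a randomized comparison create bias by itself. It mainly costs precision, and bears on bias only if baseline predicts both dropout and outcome.

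**Conclusion.** The concern holds as a mismatch between method and stated assumption. The only dose-response model is a complete-case fit, SAP 7.3 does not describe it, and it needs a stronger missingness condition than the primary MMRM. The plausible cost is about 0 to 2 points under a common outcome-dependent mechanism, and up to about 5 points if loss is strongly outcome-dependent and unequal across arms, in a direction that cannot be foreseen. These sizes rest on the assumed correlations, dropout models and true effects above; only the 20-point difference, SD 25 and 15% ceiling come from the documents. The primary analysis is unaffected. The unlisted removal of the protocol's 100% imputation check is a separate, plain omission from Table 8. The change is worth making because it is cheap and needs no new data.

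**What to change.** In SAP 9.4.4, fit E0 + Emax·f(dose) to the Week 16 posterior means and covariance from the primary Bayesian MMRM, or replace that model's Week 16 treatment parameters by E0 + Emax·f(dose). Either route brings in the earlier visits and the baseline PASI by visit terms, and puts the curve and the overlaid means on the same participants and the same missing-at-random assumption. At minimum, add baseline PASI to the current model and say in 9.4.4 that it is a complete-case analysis to which the mixed-model sentence in SAP 7.3 does not apply.

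Add a line to Table 8 stating that the 100% imputation check on this model in Protocol 7.6.1 was dropped, and why. Restoring it unchanged would not be a good substitute. Under the sign convention in Protocol 7.1.1, +100% is a doubling of PASI, (100 − 0)/25 = 4 SD above no change, and the protocol's description of who would be imputed is incomplete.

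The cost is SAP wording plus some extra programming and model checking for a sensitivity analysis. If the curve is fitted to the MMRM summaries, the DIC selection rule needs restating, because the likelihood is then that of four group means and the 4-parameter form has as many mean parameters as means.

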If the assumption of similarity between the 3 placebo cohorts is considered appropriate, the placebo cohorts will be pooled, and a single placebo control group will be used for the pairwise differences for each active dose to placebo. If the assumption of similarity is considered inappropriate, each placebo dose will be included in the model as a separate dose level and pairwise comparisons between each active dose and placebo will be performed using only the matching placebo dose data for the relevant active dose.

The adjusted posterior mean percentage change from baseline and the associated 95% HDP CrI for each treatment at Week 16 will be reported, together with the adjusted mean difference from placebo and the associated 95% HDP CrI for each active dose at each visit and the probability that each treatment difference is less than 0%, -20%, -30%, and -50%.

Model checking and diagnostic plots, including posterior density plots of the posterior samples for all parameters in the model and residual plots to evaluate the distributional assumptions underlying the model, will be produced. The assumption that data are missing at random will be evaluated by plotting the mean percentage change in PASI score against visit,

by treatment group, for the subgroups of participants who completed 16 weeks of study drug compared with those who discontinued study drug before the Week 16 visit.

If model checking and diagnostic plots show a violation of the assumptions underlying the analysis, alternative statistical methods will be considered, appropriate to the type of violation observed.

This primary analysis will be repeated using the 3 supportive estimands defined in Section 7.1.1.

If the assumption of similarity between the placebo cohorts is supported, a supplementary analysis will be performed on the percent change from baseline to Week 16 in PASI score using a dose-response model on the pooled cohorts. The log-linear, 3-parameter, and 4-parameter E_{max} models will be fitted and compared, with the best fitting model (lowest DIC) selected for use in the outputs.

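### One dose-response model is chosen by lowest DIC and reported alone, but DIC at the posterior parameter means is unreliable for the 4-parameter Emax model with four dose groups and no stated bounds, and the low-dose intervals then tend to be too narrow

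*SAP*

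**What the plan says.** SAP 9.4.4 applies if the placebo cohorts are pooled: "a sensitivity analysis will be performed on the percent change from baseline to Week 16 in PASI score", using a Bayesian dose-response model. Dose is continuous, with "values of 0, 1, 4 and 10 used to denote the number of active capsules taken". Three mean curves are fitted: log-linear in dose + 0.01, 3-parameter Emax and 4-parameter Emax. On priors, "Normal, non-informative priors will be used for the E0 and Emax parameters with mean 0 and SD 1000", and "A functional uniform prior (FUP) will be used, when required, for the ED50 and slope parameters". The SAP adds that the FUP density is based on all model parameters. It states no limits for ED50 or slope.

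The selection rule is "The best-fitting (lowest DIC) of the three models will be selected"; then, "based on the selected model, the posterior mean with associated 95% HPD CrI will be displayed", together with the differences from placebo and the probabilities that they lie below 0, -20%, -30% and -50%. Protocol 7.6.1 agrees: "with the best fitting model (lowest DIC) selected for use in the outputs". Neither document defines the effective number of parameters (pD), says what happens if it is negative, or provides for averaging.

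The SAP calls this a sensitivity analysis and the protocol calls it supplementary. Dose response and optimal dose are secondary objectives (SAP 4.1), protocol 7.6.2 rules out dose-response modelling in the secondary analyses, and SAP 7.4.3 lists this model among the interim outputs.

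**The concern.** Write D̄ for the posterior mean deviance and D(θ̄) for the deviance at the posterior means of the parameters. Then pD = D̄ − D(θ̄) and DIC = D̄ + pD. The penalty makes sense only if θ̄ gives a curve that fits about as well as a typical posterior draw.

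The 4-parameter Emax has four mean parameters for four dose groups. Many combinations of Emax, ED50 and slope give nearly the same four means, so the posterior is a long curved ridge. The point formed from the separate posterior means can lie off that ridge and draw a curve that fits badly. D(θ̄) is then large, pD turns negative, and DIC rewards the model for being poorly identified.

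At stake are the reported curve, its intervals and its threshold probabilities, above all at 1 capsule, where the three shapes differ most.

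**Working it through.** **Inputs.** SAP Section 6: effect 20 points, SD 25, 75 pooled placebo and 50 per active dose, 15% discontinuation, hence 42 per active dose and 3 × 21 = 63 placebo at Week 16. SAP 9.4.4: doses, models, priors and FUP dose grid. Assumed: plug-in DIC as above, complete data, the true curves, and the bounds.

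**The plan's own figure.** Power = Φ(Δ/[SD·√(1/n₁+1/n₂)] − 1.96), taking 5% as two-sided.
- 63 vs 42: 20/(25 × 0.1992) = 4.016; Φ(2.056) = 98.0% (stated: above 95%).
- 21 vs 42: 20/(25 × 0.2673) = 2.993; Φ(1.033) = 84.9% (stated: above 80%).

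Both reproduce. The documents give no figure for DIC selection or interval coverage.

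**Main simulation.** 400 trials per setting (Monte Carlo error up to √(0.25/400) = 2.5 points), variance unknown, 5000 draws per fit. Twelve non-null curves: six shapes (Emax with ED50 of 1 or 4, plateau, log-linear, sigmoid, linear), each with a top-dose effect of -10 or -20. A null curve was added. As the SAP gives no bounds, five readings were run, from narrow (ED50 0.01-15, slope 0.5-10) to wide (ED50 0.001-1000, slope 0.05-30), with the FUP either joint over all parameters (closest to the SAP text) or normalised given Emax. Over the non-null curves:

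| Bounds, FUP | 4-par. chosen, mean (range) | pD < 0 for 4-par., mean | 95% coverage at 1 capsule, mean (range) | Same, DIC at fitted dose means |
|---|---|---|---|---|
| Narrow, given Emax | 48% (10-80) | 4% | 75.2% (44.3-85.8) | 73.3% |
| Narrow, joint | 69% (39-88) | 13% | 80.6% (57.8-90.0) | 73.8% |
| Wide, given Emax | 55% (23-74) | 10% | 69.1% (35.2-84.5) | 68.3% |
| Intermediate, joint | 83% (57-99) | 41% | 77.9% (63.2-97.8) | 71.5% |
| Wide, joint | 89% (66-100) | 63% | 77.0% (58.0-96.8) | 71.5% |

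With wide bounds and the joint FUP, the 4-parameter model was chosen in 97-100% at a -20 effect, 66-90% at -10, and 41% under the null. Under the null it was chosen in 22% with narrow bounds and the joint FUP, but in 52% with narrow bounds and the FUP given Emax. Mean coverage was 90-92% at 4 capsules and 92-95% at 10. Under the null, coverage at 1 capsule was 91-98%.

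**One cell in full.** Wide, joint, truth exactly log-linear, effect -20. Median pD was 3.0 (log-linear), 2.7 (3-parameter) and -8.4 (4-parameter). On medians, the 4-parameter model gains 3.0 − (−8.4) = 11.4 DIC points over the true model before fit is considered. It was chosen in 97% of trials and the true model in 0%. With the deviance at the fitted dose means, the true model was chosen in 77% and the 4-parameter model in 3%.

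**Is DIC the cause of the under-coverage?** Only in part. Always using the 4-parameter model covered 62-80% on average at 1 capsule, and always using the 3-parameter model 75-81%. The log-linear form fixes the 1-capsule effect at log(1.01/0.01)/log(10.01/0.01) = 4.615/6.909 = 67% of the 10-capsule effect, whatever the data show. For the sigmoid curve (wide, joint, -20), correcting DIC but still picking one model lowered coverage from 96.5% to 34.5%. A plain unstructured difference from placebo covered 93-98%.

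**Averaging.** A second simulation used 150 trials per cell (Monte Carlo error up to √(0.25/150) = 4.1 points), SD treated as known, effect -20 and five non-null curves, 30 cells in all. With ED50 bounded at 100 or 1000, pD was negative in 43-100% of trials and the 4-parameter model was chosen in 74-100%; with ED50 ≤ 15 it was chosen in 28-89%. Coverage at 1 capsule over all bounds:
- lowest DIC, one model: 53-93%
- corrected DIC, one model: 41-91%
- average with corrected-DIC weights: 81-97%, at least as good as selection in all 30 cells, but only 81-87% for the plateau curve.

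**The case against.** The analysis is not primary. The MMRM treats dose as categorical and already gives each dose's difference from placebo, its 95% interval and the same threshold probabilities, and SAP 9.4.4 overlays the MMRM estimates on the fitted curve, so a mismatch at 1 capsule would be visible. No decision rule uses the curve. All of this stands and limits the impact.

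Three stronger readings are tempting, and the documents do not support them.
- *DIC almost always picks the 4-parameter model.* That needs wide bounds and an effect near 20 points, and even then one reading (wide bounds, FUP given Emax) stayed at 23-74% over both effect sizes. Without stated bounds, no single rate follows from the SAP.
- *DIC selection produces the narrow intervals.* Correcting DIC and still picking one model covers no better on average.
- *The FUP for ED50 has no mean.* That holds if the density is normalised given Emax, where it falls as ED50⁻². With the full gradient over all parameters, arguably what the SAP describes, it falls as about ED50⁻⁴ and the prior mean exists at fixed Emax. Identification remains weak either way.

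Averaging might also be called a matter of taste. The comparison in all 30 cells argues otherwise, though the gain is small for a plateau.

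**Conclusion.** The rule as written is unreliable and should be changed. Lowest DIC, computed at the posterior parameter means, can favour the 4-parameter model through a negative pD. The rate of choosing it depends on choices the SAP leaves open: about 75-100% in most runs with wide bounds and a 20-point effect, about 10-90% with narrow bounds, and lower for smaller effects or a null curve under most readings. After selection, nominal 95% intervals at 1 capsule under-cover for most non-null curves: about 50-95% in most settings, 35% at worst.

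A reader might infer that the primary result, or any reported difference from placebo, is compromised. It is not: the MMRM does not depend on this rule. What is affected is the plan's only dose-response model, which serves the secondary dose-response and optimal-dose objectives and is also an interim output.

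These figures rest on the assumed true curves, bounds, FUP reading and complete data, and on the plug-in definition of pD. The mechanism was not examined for other definitions of pD.

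**What to change.** In SAP 9.4.4 and protocol 7.6.1:
1. State finite bounds for ED50 and slope, and whether the FUP is joint in all parameters or normalised given Emax.
2. Compute DIC with the deviance at the posterior means of the four fitted dose means, not at the posterior means of ED50 and slope. WAIC or leave-one-out are alternatives, but were not tested here.
3. Replace single-model selection by the posterior averaged over the three fits, with weights proportional to exp(−DIC/2), and show the three separate curves beside it.
4. Say that the MMRM estimate at 1 capsule is to be read alongside the averaged curve, since coverage stays near 81-87% if the true curve is a plateau from 1 capsule.

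The cost is SAP and protocol wording and a little post-processing, because all three models are fitted anyway. Low-dose intervals will usually be somewhat wider.
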